17.2.5 Echocardiogram

If a resting transthoracic echocardiogram has not been done within 6 months prior to written informed consent at medication washout or screening, as applicable, it will be performed at screening.

17.2.6 University of California, Los Angeles, Scleroderma Clinical Trials Consortium Gastrointestinal Scale, 2.0, Questionnaire [148, 149]

The UCLA Scleroderma Clinical Trials Consortium Gastrointestinal Tract (UCLA SCTC GIT) 2.0 is a self-administered survey. The survey consists of 34 questions (Reflux 1 to 8, Distention/Bloating 9 to 12, Fecal Soilage 13, Diarrhea 14 to 15, Social functioning 16 to 21, Emotional well-being 22 to 30, Constipation 31 to 34). The items are scored on a scale from 0 to 3, where 0 indicates better health and 3 indicates worse health, except for questions 15 and 31, which are scored as 0 (better health) and 1 (worse health). Scores from all scales except the constipation scale are averaged to form a total GIT score from 0 (no gastrointestinal problems) to 3 (most severe) that captures overall burden of severity of SSc-associated GIT involvement.

The UCLA SCTC GIT 2.0 questionnaire will be used to obtain the participant's assessment of

the frequency of GI symptoms in the preceding 7 days and how those symptoms affected his/her life. The questionnaire will be administered during screening (see 8.2.1 Study Population Exclusion Criteria), at study Day 1, and at each subsequent study visit every 28 days (weeks 4-24). For the extension study, the questionnaire will be administered at study day 84 (week 36) and study day 168 (week 48) office visits.

17.3 Study Measures for the Secondary Objective to Assess the Clinical Efficacy of Ixazomib

17.3.1 High-Resolution Computed Tomography Scan

An HRCT chest scan will be used at screening to confirm eligibility. A HRCT chest scan may be used for this purpose if completed within 3 months prior to the date of written informed consent at either medication washout or screening, as applicable. The HRCT must demonstrate features consistent with SSc-ILD as confirmed by review of the HRCT images by Mayo radiology study staff. If the previous HRCT chest study is determined to be technically inadequate or cannot be made available for review by Mayo radiology study staff, or if the HRCT chest scan was performed more than 3 months prior to signing of written informed consent, a HRCT chest scan will be obtained during study screening. The extent of scleroderma lung involvement identified on the HRCT study, limited or extensive, will be scored according to the Goh criteria [6]. A follow-up HRCT chest scan will be obtained at the study visit on day 168 (week 24). For the extension study, HRCT chest scan will be obtained at study day 168 (week 48).

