6.2 Secondary Objective

To determine the clinical efficacy of ixazomib 4 mg taken orally on days 1, 8, and 15 of a 28-day treatment cycle repeated for 6 cycles when administered to adult patients with scleroderma-related ILD as assessed by:

1. ACR CRISS (American College of Rheumatology Composite Response Index for clinical trials early diffuse cutaneous Systemic Sclerosis) [150].
2. Each of the individual components of ACR CRISS: mRSS (modified Rodnan skin score), FVC % predicted, HAQ-DI (Health Assessment Questionnaire-Disability Index), PtGA (Patient Global Assessment), MDGA (Physician Global Assessment).
3. DLCO % predicted.
4. High resolution CT (HRCT) chest scan ILD severity using the Goh scoring method [6].
5. Additional patient reported outcome Mahler Baseline/Transitional Dyspnea Index (Mahler BDI/TDI).

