7.0 STUDY DESIGN

7.1 Overview

This is a phase 2 open-label, safety and tolerability pilot study of oral ixazomib in patients with scleroderma-ILD (SSc-ILD). Planned enrollment will be 12 patients who have been seen in the Mayo Clinic Arizona Scleroderma program among whom will be 6 participants already taking SSc-ILD background medication mycophenolate (MMF) at stable dose for at least 3 months, and 6 participants who either have not taken a SSc-ILD background medication within 3 months of study screening or by the time of study screening will complete medication washout of medications being taken for SSc-ILD other than MMF. The number of study candidates needing to washout medications other than MMF is anticipated to be very low based on the low prevalence of medicines other than MMF used clinically for the treatment of scleroderma-ILD. No study candidate already taking MMF will be asked to wash out MMF. Eligible participants include male and female adult patients at least 18 years of age, fulfilling the 2013 American College of Rheumatology (ACR)/European League Against Rheumatism (EULAR) criteria for systemic sclerosis/scleroderma [151] and having disease duration \leq 60 months based on first non-Raynaud's phenomenon manifestation. ILD is based on features observed from the participant's HRCT chest scan obtained within 3 months prior to either medication washout or screening visit, as applicable. Studyscreening

will include pulmonary function testing demonstrating FVC \geq 45% predicted and DLCO \geq 40% predicted, which will also be determined to be stable measurements as compared with previous pulmonary function testing obtained clinically within the prior 3-12 months. For the 6 study participants who are taking stable dose background MMF, the MMF will be continued at the same dose during the study. MMF will be prescribed as routine clinical care and will not be provided as part of the study. All 12 participants will be administered oral ixazomib. Ixazomib dose modification or interruption will be allowed for safety or tolerability reasons at any time during the study. Any patient who permanently and prematurely discontinues study treatment will also be discontinued from the study.

There are four study periods (all durations are in calendar days):

- **Washout Period:** \leq 90 days:
 - **Participants who are taking background SSc-ILD medication other than MMF at screening:**

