8.0 STUDY POPULATION

8.1 Inclusion Criteria

Patients who meet *all* of the following criteria are eligible to participate in the study:

8.1.1 Demographic Characteristics:

1. Male and female patients, age ≥ 18 years at time of signing informed written consent

8.1.2 SSc and SSc-ILD Related Criteria:

2. Confirmed diagnosis of diffuse cutaneous systemic sclerosis/scleroderma fulfilling the 2013 American College of Rheumatology (ACR)/European League Against Rheumatism (EULAR) criteria for systemic sclerosis/scleroderma [151].
3. Disease duration ≤ 60 months defined as the time from the first non-Raynaud's phenomenon manifestation.
4. mRSS ≥ 15 and ≤ 45
5. Diagnosis of SSc-ILD based on a HRCT chest scan completed within 3 months prior to the date of written informed consent at medication washout or screening, as applicable. The HRCT chest scan must demonstrate features consistent with SSc-ILD, as confirmed following review of the HRCT images by Mayo radiology study staff. If the HRCT chest study is determined to be technically inadequate (for example, prone imaging not included), or cannot be made available for review by Mayo radiology study staff, or if the HRCT chest was performed more than 3 months prior to signing of written informed consent, a HRCT chest scan will be obtained during study screening.

6. Screening pulmonary function testing demonstrating FVC \geq 45% predicted and DLCO \geq 40% predicted. Pulmonary function testing previously completed as part of clinical care within the prior 3-12 months will be used to compare screening results with prior testing to determine there has not been an interim decline of FVC \geq 15 % predicted or decline of DLCO \geq 15% predicted. Only if both FVC % predicted and DLCO % predicted are observed clinically stable will the patient be considered eligible for participation.
7. Screening resting transthoracic echocardiogram within 6 months of providing written informed consent at medication washout or screening, as applicable, demonstrating estimated right ventricular systolic pressure of \leq 40 mm Hg, no evidence of right atrial or right ventricular enlargement, and left ventricular ejection fraction \geq 40%.
8. At study entry, the participant is either not taking any background SSc-ILD medication or is taking background MMF, as described below:
 - a. Not on background SSc-ILD medication**

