24.2 Hypothesis Testing

No formal hypothesis testing will be done.

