24.6.2 Additional Assessments for Clinical Efficacy

Analysis of these additional efficacy assessments will be based on the safety population. Clinical efficacy assessments will include each of the individual components of ACR CRISS as follows:

- mRSS (modified Rodnan skin score)
- FVC % predicted
- HAQ-DI (Health Assessment Questionnaire-Disability Index)
- PtGA (Patient Global
- MDGA (Physician Global Assessment)

Additional clinical efficacy measures include:

- DLCO % predicted
- HRCT chest scan ILD severity using the Goh scoring method
- Patient reported outcome Mahler Baseline/Transitional Dyspnea Index (Mahler BDI/TDI).

The results of mRSS score and changes from baseline at study day 84 (week 12) and study day 168 (week 24) will be summarized without imputation for missing values.

The percent predicted FVC and DLCO results and change from screening at study day 28 (week 4), day 56 (week 8), day 84 (week 12), day 112 (week 16), day 140 (week 20) and study day 168 (week 24) will be summarized descriptively without imputation for missing values. Total lung capacity results and change from screening at study day 84 (week 12) and study day 168 (week 24) will be summarized descriptively without imputation for missing values.

HRCT chest scan Goh scoring of ILD severity and change from baseline at study day 168 (week 24) will be summarized descriptively.

The results for each of the disease-status scales Mahler BDI/TDI, SHAQ, PtGA and MDGA and changes from baseline at study day 84 (week 12) and study day 168 (week 24) will be summarized descriptively without imputation for missing values.

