25.5.2.2 Additional Assessments for Clinical Efficacy (see Section 24.6.2)

As per Section 24.6.2, the results of mRSS score and change from baseline for study day 84 (week 12) and day 168 (week 24) of the initial study are summarized without imputation for missing values for both treatment groups. Additional results of mRSS and change from baseline will be summarized without imputation for missing values for both treatment groups for extension study day 84 (week 36) and extension study day 168 (week 48).

As per Section 24.6.2, the percent predicted FVC and DLCO results and change from screening at study day 28 (week 4), day 56 (week 8), day 84 (week 12), day 112 (week 16), day 140 (week 20) and day 168 (week 24) of the initial study are summarized descriptively without imputation for missing values for both treatment groups. Additional percent predicted FVC and DLCO results and change from screening will be summarized descriptively without imputation for missing values for both treatment groups for extension study day 84 (week 36) and extension study day 168 (week 48).

As per Section 24.6.2, total lung capacity results and change from screening at study day 84 (week 12) and study day 168 (week 24) of the initial study are summarized descriptively without imputation for missing values for both treatment groups. Additional total lung capacity results and change from screening will be summarized descriptively without imputation for missing values for both treatment groups for extension study day 84 (week 36) and extension study day 168 (week 48).

As per Section 24.6.2, HRCT chest scan Goh scoring of ILD severity and change from baseline at initial study day 168 (week 24) are summarized descriptively for both treatment groups. HRCT chest scan Goh scoring of ILD severity and change from both baseline and initial study day 168 (week 24) will be summarized descriptively for extension study day 168 (week 48) for both treatment groups.

As per Section 24.6.2, the results for each of the disease-status scales Mahler BDI/TDI, SHAQ, PtGA and MDGA and changes from baseline at study day 84 (week 12) and study day 168 (week 24) of the initial study are summarized descriptively without imputation for missing values for both treatment groups. The results for each of these disease-status scales Mahler

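### The only HRCT score the plan describes is limited versus extensive, yet it is summarised as change from baseline; percent extent should be recorded and analysed beside it

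*Combined protocol and SAP*

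**What the plan says.** Section 6.2 lists the measure fourth of five items under the secondary (clinical efficacy) objective: "High resolution CT (HRCT) chest scan ILD severity using the Goh scoring method". Sections 16.2.2 and 17.3.7 describe it in the same terms. The only account of what is written down is in 17.3.1: "The extent of scleroderma lung involvement identified on the HRCT study, limited or extensive, will be scored according to the Goh criteria". Scans are taken at screening and week 24, with a further scan at week 48 in the extension.

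For analysis, 24.6.2 states: "HRCT chest scan Goh scoring of ILD severity and change from baseline at study day 168 (week 24) will be summarized descriptively". For the extension, 25.5.2.2 states: "HRCT chest scan Goh scoring of ILD severity and change from both baseline and initial study day 168 (week 24) will be summarized descriptively". Section 25.5.4.2 plans the same two changes for the extension's final post-discontinuation visit.

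On entry, 8.1 requires of the scan: "The HRCT chest scan must demonstrate features consistent with SSc-ILD". It sets no upper limit on HRCT extent. Section 7.1 gives the size of the trial, "Planned enrollment will be 12 patients", six on background MMF and six on no background ILD medication. Section 24.2 adds: "No formal hypothesis testing will be done".

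**The concern.** A two-level score leaves little room for a change from baseline. It has only three outcomes (up, down, same), and each participant can reach only two of them, depending on the starting category. Because entry is not capped on extent, participants already in the upper category can enrol, and for them the HRCT record has no way to show progression.

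The plan gives its other efficacy scales more resolution: the skin score grades 17 sites from 0 to 3, the global assessments run from 0 to 10, and FVC and DLCO are percent predicted. HRCT is the only lung-imaging outcome in a population defined by lung disease, and it is the one without a graded scale. Since no hypothesis test is planned, the descriptive summaries are the whole efficacy output, so their resolution matters. A percent extent not recorded at reading can be recovered only by reading the scan again.

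**Working it through.** The plan states no HRCT figure, expected change or category split, so there is nothing of its own to reproduce. The check has a logical part and an illustrative part.

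**Logic (no assumptions beyond a two-category record)**

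| Category at entry | Can be recorded later as | Cannot be recorded |
|---|---|---|
| Limited | limited, extensive | better than at entry |
| Extensive | extensive, limited | worse than at entry |

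If k of the 12 enter as extensive, recorded worsening is impossible for k and recorded improvement for 12 − k. Any movement that stays on one side of the cut counts as no change.

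**Illustration 1: bivariate normal extent.** Let X be extent at baseline and Y at follow-up, in baseline SD units, with correlation ρ and mean worsening s. The cut c is placed so that a share f is extensive at entry.

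P(category changes) = P(X < c, Y ≥ c) + P(X ≥ c, Y < c)

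Assumed ranges, none of them from the documents: f = 25% to 75%, ρ = 0.70 to 0.95, s = 0 to 0.5 SD.

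| Setting | P(change) | Expected of 12 | P(none of 12 change) |
|---|---|---|---|
| Lowest: f = 25% or 75%, ρ = 0.95, s = 0 | 0.080 | 0.96 | 0.366 |
| Middle: f = 50%, ρ = 0.90, s = 0 | 0.144 | 1.72 | 0.156 |
| Highest: f = 50%, ρ = 0.70, s = 0.5 | 0.289 | 3.47 | 0.017 |

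The middle row can be checked by hand: with a median cut and no shift the formula reduces to arccos(ρ)/π = arccos(0.90)/π = 0.144. So 71% to 92% of participants would show no recorded change. The extension summaries are by treatment group. If all six in a group were scanned, the expected number changing would be 0.5 to 1.7 (half of 0.96 and 3.47), and in the middle setting the chance that none of six changes is 0.395.

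**Illustration 2: even spread.** If percent extent is spread evenly over a range of width w, the cut lies inside it, and everyone worsens by d points, the share crossing is d/w.

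- 5–50%, d = 5: 5/45 = 11.1%, or 1.3 of 12
- 5–50%, d = 10: 10/45 = 22.2%, or 2.7 of 12
- 5–40%, d = 5: 5/35 = 14.3%, or 1.7 of 12
- 10–60%, d = 5: 5/50 = 10.0%, or 1.2 of 12

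In this second model everyone worsens, yet fewer than 3 of 12 are recorded as worse. The two models are different in kind and both fall within about 1 to 3.5 of 12.

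**The case against.** The strongest reply is that the plan does not say percent extent is discarded. It cites a published scoring method for HRCT severity, and what that method records is set out in the cited paper, not here. This stands: a reader might infer that the plan commits to a bare dichotomy, but the text neither includes nor excludes a percent. It does not settle the matter, because the only result named is the category and no section defines change on it.

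A reader might also infer that real lung change would be invisible in most participants. The documents do not support that. FVC and DLCO percent predicted are summarised at six visits to week 24 and again at weeks 36 and 48, and total lung capacity at weeks 12, 24, 36 and 48. Only change in the HRCT record is at issue, and any count of participants rests on assumed distributions and an assumed cut.

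Two further inferences fail. One is that the reader knows the order of the scans: masking to date or treatment is unspecified, not stated to be absent. The other is that the Goh category decides eligibility: entry requires features of the disease, not a category.

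Finally, this is a secondary, descriptive measure in a 12-patient safety pilot, and percent extent would also be only descriptive. That is fair and limits the weight of the point, but it does not make the coarser summary preferable when the finer one costs so little.

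**Conclusion.** The point holds in conditional form. The only HRCT score described has two levels, and three analysis sections summarise its change. If that category is all that is kept, worsening cannot be recorded for anyone extensive at entry, improvement cannot be recorded for anyone limited at entry, and change within a category is lost. That much follows by logic.

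The size does not follow from the documents. Under the assumed ranges (25% to 75% extensive at entry, correlation 0.70 to 0.95, mean worsening 0 to 0.5 SD), about 1 to 3.5 of 12 would change category. The safety objective is untouched and lung function remains well covered. This is a cheap improvement to a secondary outcome rather than a flaw in the trial's main purpose.

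**What to change.** - **Section 17.3.1:** have the existing radiology study staff record percent extent beside the limited/extensive category at every scan. If they already do, say so.
- **Sections 24.6.2, 25.5.2.2 and 25.5.4.2:** summarise percent extent and its change from baseline (and from week 24 in the extension). Show the category as a baseline-by-follow-up shift table.

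The cost is one extra field per reading, with no added scan, visit or staff. The drawback is that visual percent extent carries some reader variability, so small individual changes should be read with caution.

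Reading each participant's scans together, with dates and order masked, would be an optional addition. It covers up to 12 × 3 = 36 scans and is not needed for the core change.

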17.3.2 Pulmonary function testing, Spirometry, and DLCO Measurements

All equipment, procedures, and personnel qualifications for the assessment of lung function are based on the recommendations of the American Thoracic Society/ European Respiratory Society. Complete pulmonary function testing includes lung volumes and DLCO. Spirometry includes total lung capacity (TLC), forced expiratory volume in 1 second [FEV1] and FVC % predicted; DLCO measurements also will be obtained. Bronchodilator use will be prohibited in the 24 hours before spirometry testing. Complete pulmonary function tests will be obtained at screening; study visit day 84 (week 12) and study visit day 168 (week 24). Spirometry and DLCO will be obtained at study visit day 28 (week 4), day 56 (week 8), day 112 (week 16), and day 140 (week 20). For the extension study, complete pulmonary function will be obtained at study day 84 (week 36) and study day 168 (week 48).

17.3.3 Disease-Status Scales

The following disease-status scales will be used to obtain the participant's evaluation of the symptoms of SSc and SSc-ILD and/or the effect of those symptoms on his/her quality of life:

- **Mahler Baseline/Transitional Dyspnea Index** (Mahler BDI/TDI): patient's assessment of the severity of dyspnea.
- **Scleroderma Health Assessment Questionnaire** (SHAQ): patient's assessment of how the disease affects his or her ability to function in daily life in the eight domains of the Health Assessment Questionnaire Disability Index (HAQ-DI). These domains include dressing and grooming, arising, eating, walking, hygiene, reach, grip, and activities, along with a visual analog scale (VAS) rating pain severity;

SHAQ additionally includes five scleroderma-specific VAS scales related to Raynaud's, digital fingertip ulcers, gastrointestinal symptoms, lung symptoms/shortness of breath, and patient overall disease severity assessment.

- **Patient Global Assessment of Disease Activity (PtGA):** Patient's Global Assessment is a patient-reported outcome that represents the subject's overall assessment of his or her current health (Question- how was your overall health in the last week) on a 11- point Numeric rating scale anchored at 0 (excellent) to 10 (extremely poor), with higher scores indicating worse disease in terms of severity, damage, or overall disease.

The disease-status scales will be completed at study Day 1, day 84 (week 12) and day 168 (week 24) but will be administered more frequently if clinically indicated. For the extension study, the disease-status scales will be completed at study day 84 (week 36) and study day 168 (week 48) office visits.

17.3.4 Physician's Global Assessment (MDGA)

The MDGA evaluates the overall impact of SSc on the participant as assessed by the physician on a 11-point Numeric rating scale from 0 (excellent) to 10 (extremely poor) (Question - how was your patient's overall health in the last week), with higher scores indicating worse disease in terms of severity, damage, or overall disease.

MDGA will be performed study Day 1, day 84 (week 12) and day 168 (week 24) but will be administered more frequently if clinically indicated. For the extension study, MDGA will be performed at study day 84 (week 36) and study day 168 (week 48) office visits.

To address intra-reader variability in MDGA and to increase interpretability of efficacy measures, MDGA will be performed by the same qualified individual during the study, to the extent possible.

17.3.5 Modified Rodnan Skin Score (MRSS):

MRSS is clinician's assessment of skin thickness at 17 prespecified sites on the body with the thickness at each site scored from 0 (uninvolved) to 3 (severe thickening).

The MRSS will be performed during screening (see 8.2.1 Study Population Exclusion Criteria), study day 1, day 84 (week 12) and day 168 (week 24). For the extension study, the MRSS will be performed at study day 84 (week 36) and study day 168 (week 48) office visits.

To address intra-reader variability, mRSS will be performed by the same qualified individual during the study, to the extent possible.

17.3.6 ACR CRISS (American College of Rheumatology Composite Response Index for clinical trials in early diffuse cutaneous Systemic Sclerosis) [150]

ACR CRISS incorporates multisystem involvement in diffuse cutaneous systemic sclerosis and includes the patient's perspective and the impact of the disease on functional disability.

The ACR CRISS is calculated as a 2-step process. The first step evaluates clinically significant decline in renal or cardiopulmonary involvement that is related to SSc and requires treatment. Subjects are considered to be not improved by their treatment if they develop

any one of these four outcomes following treatment, if it appears linked to the disease process:

- New scleroderma renal crisis.
- Decline in FVC % predicted $\geq 15\%$ (relative) confirmed by another FVC % predicted within a month; and if so, a HRCT chest scan to confirm progression ILD.
- A new decline of left ventricular ejection fraction to 45% or less attributable to scleroderma and requiring treatment.
- New onset of pulmonary arterial hypertension attributable to SSc that requires treatment (pulmonary arterial hypertension is defined as mean pulmonary artery pressure ≥ 25 mmHg at rest, an end-expiratory pulmonary wedge pressure ≤ 15 mmHg, and a pulmonary vascular resistance > 3 Wood units).

If any one of these is present, the participant is classified as not improved regardless of changes in other parameters.

The second step assesses participants and calculates the predicted probability of improvement based on changes in the mRSS, FVC % predicted, patient global assessment, physician global assessment, and HAQ-DI.

ACR CRISS will be applied study Day 1 (using FVC % predicted at screening within 21 days), study day 84 (week 12) and study day 168 (week 24). For the extension study ACR CRISS will be applied study day 84 (week 36) and study day 168 (week 48).

